7.7.3 Non-serious Adverse Events

Following the subject's written consent to participate in the study, the investigator will begin collecting non-serious AE (NSAE) information. All identified NSAEs must be recorded and described on the AE case report form. If an ongoing NSAE worsens in its intensity, or if its relationship to the investigational product changes, a new NSAE entry for the event should be completed. NSAEs should be followed to resolution or stabilization, or reported as SAEs if they become serious. Follow up is also required for drug-related NSAEs that cause interruption or discontinuation of investigational product, or those that are present at the end of study participation. Subjects with drug-related NSAEs at study completion should receive post-treatment follow up as appropriate.

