8.1.2 Secondary Endpoints

The secondary endpoints of the study are:

- The change from baseline of VO₂MAX at the end of study-drug dosing Period 1 compared to the change from baseline at the end of study-drug dosing Period 2.
- An evaluation of the change in VO₂MAX at the end of study-drug dosing Period 1 compared to baseline will be performed.
- The change from baseline of the QTcF interval at the end of study-drug dosing Period 1 compared to the change from baseline at the end of study-drug dosing Period 2

- The change from baseline at the end of study-drug dosing Period 2 in the Six-Minute Walk Test (6MWT) and change from baseline at the end of study-drug dosing Period 1 compared to the change from baseline at the end of study-drug dosing Period 2
- Safety data (AEs, ECG abnormalities, routine laboratory safety test of blood, vital signs, and concomitant medication and patient withdrawals) during study-drug dosing Period 1 compared to study-drug dosing Period 2

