3.2 Safety Variables

3.2.1 Adverse Events

Adverse events (AEs) were to be spontaneously reported or elicited during open-ended questioning, examination, or evaluation of a patient. The protocol (section 7.1) defines an AE as any untoward medical occurrence associated with the use of a drug in humans, whether or not considered drug related.

The following information was to be captured for all AEs:

- Start date

- End date (or ongoing status, if ongoing at the end of study)
- Outcome (Recovered/Resolved; Recovered/Resolved with Sequelae; Recovering/Resolving; Not Recovered/Not Resolved; Fatal; Unknown)
- Relationship to study treatment (Definitely Related; Probably Related; Possibly Related; Unrelated)
- Action taken with study treatment (Drug Withdrawn; Drug Interrupted; Dose Reduced; Dose Not Changed; Dose Increased; Other; Not Applicable)
- Any other action taken (No; Yes)
- Caused study discontinuation (No; Yes)
- Severity (Mild; Moderate; Severe)
- Seriousness (No; Yes)
- Adverse Device Effects (No; Yes)
- Is the event an overdose (No; Yes)
- Is the event a cancer event (No; Yes)

If the investigator deemed the AE to be serious, the reason(s) for being considered serious would be recorded in the eCRF.

AEs will be coded using the Medical Dictionary for Regulatory Activities (MedDRA).

A treatment-emergent adverse event (TEAE) is defined as any AE with a recorded start date on or after the date of the first dose of study medication. Treatment emergent (TE) status of AEs with a partial start date will be determined using available incomplete date information. For example, if the AE has a missing day field but the non-missing month and year fields place the start of the AE after the start of study medication, then the AE will be designated TE. For AEs where the available partial date information is inconclusive (for example, missing day but available month and year are equal to the month and year of start of study medication) then the AE will be classified as TE. In particular, AEs with a completely missing start date will be assumed to be TE (unless the AE stop date places the AE prior to starting treatment).

TEAEs will be split further according to whether the AE start date occurred during Period 1 or Period 2 of the Treatment Epoch, or during the Follow-up Epoch.

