8.2 Adverse Events

Treatment-emergent AEs (TEAEs) occurring in patients from the Safety Population will be presented in data listings with an indication of whether the AE start date occurred during Period 1, Period 2, or the Follow-up Period. Any AEs that were recorded in the CRF from patients who were not included in the Safety Population will be listed separately and will not be included in any subsequent listings or tables.

A summary overview of TEAEs will be provided, which will present the number and percentage of patients satisfying each of the following categories. This table will be presented for Period 1 and Period 2 (see 3.2.1 for derivation) separately and for Period 1 and Period 2 combined and for the Follow-up Period, using the Safety Population.

- Any TEAEs
- Maximum severity of TEAEs
- Study drug-related TEAEs
- All TE SAEs
- All TE study drug-related TE SAEs
- TEAEs leading to death
- TEAEs leading to withdrawal of study medication

The number and percentage of patients with TEAEs will be summarized by their MedDRA preferred term within system organ class. This will be presented for Period 1 and Period 2 separately and for Period 1 and Period 2 combined and for the Follow-up Period, using the Safety Population. In this summary, any patients reporting multiple episodes of the same TEAE (i.e. same preferred term) within a single period, will be counted once. It is acknowledged that any conclusions that arise from a comparison of AEs reported during Period 1 and Period 2 may be limited due to the consecutive nature of the periods. A similar summary will be provided for study drug-related TEAEs.

The number and percentage of patients with TEAEs will be summarized by reported severity (*Severity = 'Mild', 'Moderate', 'Severe'*) within each MedDRA preferred term within system organ class. This will be presented for Period 1 and Period 2 separately and for Period 1 and Period 2 combined and for the Follow-up Period, using the Safety Population. In this summary, any patients reporting multiple episodes of the same TEAE (i.e. same preferred term) within a single period, will be counted once against the most severely reported category.

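### AE tables count each event only in the period where it starts, so AEs persisting unchanged from Period 1 are absent from Period 2 and the AE burden at the higher range is understated

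*SAP*

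**What the plan says.** Protocol 8.1.2 makes safety data a secondary endpoint, to be assessed "during study-drug dosing Period 1 compared to study-drug dosing Period 2". Every patient passes through Period 1 (target 100-300 ng/mL) and then Period 2 (target 300-500 ng/mL).

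SAP 3.2.1 defines a treatment-emergent AE as "any AE with a recorded start date on or after the date of the first dose of study medication" and then allocates it by onset: "TEAEs will be split further according to whether the AE start date occurred during Period 1 or Period 2", or during follow-up. SAP 8.2 applies this to the overview: "This table will be presented for Period 1 and Period 2 (see 3.2.1 for derivation) separately and for Period 1 and Period 2 combined". The preferred-term and severity tables have the same period columns. The listing also flags onset only, "with an indication of whether the AE start date occurred during Period 1, Period 2, or the Follow-up Period".

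Protocol 7.7.3 says when a continuing non-serious event gets a further record: "If an ongoing NSAE worsens in its intensity, or if its relationship to the investigational product changes, a new NSAE entry" is to be completed. SAP 3.2.1 also lists, among the items captured for every AE, "End date (or ongoing status, if ongoing at the end of study").

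SAP 8.2 carries one caution: "It is acknowledged that any conclusions that arise from a comparison of AEs reported during Period 1 and Period 2 may be limited", which it attributes to the periods being consecutive. It does not mention the start-date rule.

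**The concern.** The endpoint asks what happened to patients during each period. The tables show what began in each period. The two differ for an AE that starts in Period 1 and continues at the same grade and attribution. The patient has it while at the higher range, but no Period 2 record exists and the Period 2 column does not count it. While that AE continues, the same patient also cannot contribute a new onset of the same preferred term.

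Because the order is the same for everyone, the omission always falls on the higher range. Protocol 2.8 presents the study as confirming a regimen for Phase 3 and raises the possibility that lower concentrations give equal efficacy with better safety. A Period 2 column that leaves out persisting AEs is therefore incomplete on the question the trial is meant to inform.

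Other safety data are handled differently. SAP 8.5 counts patients outside a vital-sign threshold at any visit in each period, and the SAP 8.6 shift tables use any ECG in each period. A persisting abnormality there is counted in both periods.

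**Working it through.** The plan states no AE rate, persistence rate or tolerability figure, so there is nothing of its own to reproduce. The check is a counting argument followed by an illustration.

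**Counting check.** Take one AE that starts in Period 1 and continues unchanged to the end of Period 2. Under SAP 3.2.1 and 8.2 it scores 1 in Period 1, 0 in Period 2 and 1 in the combined column. Protocol 7.7.3 creates no second record, because neither intensity nor attribution changed.

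**Illustration for one preferred term.** Assumed inputs, none from the documents:
- p = chance of onset in a period, equal in both periods (no dose effect)
- s = share of Period 1 events still ongoing in Period 2
- a patient with an ongoing event cannot have a new onset of it; a patient whose event resolved can have a recurrence, at the same p
- everyone enters Period 2

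Formulas:
- Period 1 = p
- Period 2 by start date = p(1 − ps)
- Period 2 by events present = ps + p(1 − ps)

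At p = 0.2 and s = 0.5, ps = 0.10. Start date gives 0.2 × 0.90 = 0.180, and events present gives 0.10 + 0.18 = 0.280. At p = 0.2 and s = 0.8, ps = 0.16. Start date gives 0.2 × 0.84 = 0.168, and events present gives 0.16 + 0.168 = 0.328.

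| p | s | Period 1 | Period 2, start date | Period 2, present |
|---|---|---|---|---|
| 0.1 | 0.5 | 10.0% | 9.5% | 14.5% |
| 0.2 | 0.5 | 20.0% | 18.0% | 28.0% |
| 0.2 | 0.8 | 20.0% | 16.8% | 32.8% |
| 0.3 | 0.5 | 30.0% | 25.5% | 40.5% |
| 0.5 | 0.5 | 50.0% | 37.5% | 62.5% |

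With no dose effect, the start-date column puts Period 2 below Period 1 by p − p(1 − ps) = p²s, and leaves out ps of persisting burden. For p from 0.1 to 0.5 and s from 0.25 to 1.0, the shortfall is 0.25 to 25 points and the omitted burden is 2.5 to 50 points.

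**Does the rule fix the direction of the comparison?** Take the planned 33 patients, with 10 onsets in Period 1 (30.3%) of which 6 persist.
- With 6 new onsets in Period 2, the table shows 6/33 = 18.2%, although (6 + 6)/33 = 36.4% had the event during Period 2.
- With 12 new onsets, the table shows 12/33 = 36.4%, above the 30.3% of Period 1.

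So Period 2 can still look worse.

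**Would presence counts alone be neutral?** No. Under equal onset risk they exceed Period 1 by ps + p(1 − ps) − p = ps(1 − p). At p = 0.2 and s = 0.5 this is 0.10 × 0.8 = 8 points against Period 2, compared with 0.04 × 0.5 = 2 points in its favour under the start-date rule.

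**The case against.** The strongest reply is that both columns measure the same thing. AEs already ongoing at first dose are not treatment-emergent, so Period 1 is onset-only too, and an onset-to-onset comparison is coherent. In the main illustration the start-date shortfall is only 2.0 to 3.2 points, about one patient in 33. Worsening non-serious events are re-entered, the combined column keeps every event, and the SAP already cautions about the comparison. The AE tables are descriptive, and no test or decision rule depends on them. In the any-TEAE row of the overview, a patient with a persisting AE still counts in Period 2 if any other AE begins there.

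Much of this stands. A reader might infer that the rule makes the higher range look better tolerated by construction. The documents do not support that, because a rise in onsets would appear in the Period 2 column. A reader might also treat only the 80% never affected as at risk in Period 2, giving 0.8 × 0.2 = 16%. That ignores recurrence in patients whose event resolved. SAP 8.2 collapses repeat episodes only within one period, so a recurrence in Period 2 does count.

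What the reply does not answer is the omission itself. The combined column cannot show at which range an AE was present. Re-entry covers only worsened or re-attributed non-serious events. The caution states neither the rule nor its direction. Period 1 starts drug-free, whereas Period 2 starts with patients who may already have drug-period AEs, so the two columns do not draw on comparable patients at risk.

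**Conclusion.** The point holds as an understatement of AE burden in Period 2. AEs that persist unchanged from Period 1 are missing from the Period 2 column, although the secondary endpoint concerns safety during each period. The omission works in favour of the higher range but does not determine how the comparison comes out.

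The size in this trial cannot be computed, because the documents give no AE or persistence rates. With an assumed onset risk of 0.2 in each period, the table would show 18.0% in Period 2 while 28.0% had the AE if half of Period 1 events persist, and 16.8% against 32.8% if 80% persist. Period 1 shows 20.0% in both cases. These figures assume no dose effect, recurrence at the same risk, and no dropout before Period 2.

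A reader might also conclude that presence counts should replace onset counts. That does not follow. Presence counts carry Period 1 events forward and, in the same illustration, show 20.0% against 28.0% with no dose effect at all.

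**What to change.** Keep the start-date tables and label their period columns as new onset. Add to SAP 8.2, for the overview, preferred-term and severity tables, the number and percentage of patients with:

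- (a) a TEAE ongoing at the start of Period 2
- (b) a TEAE present at any time during Period 2

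Derive both from the start date and the end date or ongoing status already collected, and state a simple rule for partial end dates. Extend the SAP 8.2 caveat to say that events are allocated by start date, that unchanged persisting AEs are therefore left out of the Period 2 onset column, and that this understates AE burden at the higher range. State also that onset and presence are to be read side by side, and that presence counts alone will not be used for the Period 1 versus Period 2 comparison.

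The cost is programming and longer tables, with no new data collection. The drawbacks are reliance on AE end dates, which may be incomplete, and accumulation of earlier events in the presence counts.

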3.2.2 Safety Laboratory Evaluations

Serum Chemistry

Blood samples were to be obtained for routine serum chemistry safety tests at Screening, and repeated at the end of Period 1 (Week 8), at the end of Period 2 (Week 16) and at Follow-up (planned for Week 20) visit. The following safety chemistry parameters levels were to be assessed by a central laboratory:

- Sodium [mmol/L]
- Potassium [mmol/L]
- Bicarbonate [mmol/L]
- Chloride [mmol/L]
- Calcium [mmol/L]
- Phosphorus [mmol/L]
- Glucose [mmol/L]
- Creatinine [μ mol/L]
- BUN [mmol/L]
- Creatine Kinase [U/L]
- Uric acid [μ mol/L]
- Albumin [g/L]
- Total protein [g/L]
- AST (SGOT) [U/L]
- ALT (SGPT) [U/L]
- Alkaline phosphatase [U/L]
- Total bilirubin [μ mol/L]
- Lactate dehydrogenase (LDH) [U/L]
- Total cholesterol [mmol/L]

The Baseline value for each parameter will be identified as the last assessment value taken prior to the start of study medication. For most parameters and most patients, this will be taken as the Screening assessment, however, if any patients have an unscheduled assessment after their Screening assessment and before starting study medication, this will be used.

The change and percentage change from Baseline to the end of Period 1 (Week 8), end of Period 2 (Week 16) and Follow-up (Week 20) assessment will also be derived.

For transaminases, any assessments that are outside the following upper limit of normal (ULN) threshold multiples will be identified electronically in the analysis dataset:

AST (SGOT) [U/L]	> 3 x ULN
ALT (SGPT) [U/L]	> 3 x ULN
Alkaline phosphatase [U/L]	> 2.5 x ULN
Total bilirubin [mg/dL]	> 2 x ULN

Complete Blood Count

Blood samples were to be obtained for complete blood count at Screening, and repeated at the end of the study, Period 2 (Week 16), and Follow-up (Week 20) assessment. The following parameters levels were to be assessed by a central laboratory:

- Hemoglobin [g/L]
- Hematocrit [%]
- Red blood cells (RBC) [$10^{12}/L$]
- MCV [fL]
- MCH [pg]
- MCHC [g/L]
- White blood cells [$10^9/L$]
- Neutrophils [$10^9/L$ and %]
- Lymphocytes [$10^9/L$ and %]
- Monocytes [$10^9/L$ and %]
- Eosinophils [$10^9/L$ and %]
- Basophils [$10^9/L$ and %]
- Platelets [$10^9/L$]

The Baseline value for each parameter will be identified as the last assessment value taken prior to the start of study medication. For most parameters and most patients, this will be taken as the Screening assessment, however, if any patients have an unscheduled assessment after their Screening assessment and before starting study medication, this will be used. The change and percentage change from Baseline to the end of Period 1 (Week 8), end of Period 2 (Week 16), and Follow-up (Week 20) assessment will also be derived.

Biomarker Hemoglobin A1c Testing

Sampling for biomarker levels of hemoglobin A1c was to be performed at Screening, and repeated at the end of the Period 1 (Week 8), at the end of Period 2 (Week 16), and at the Follow-up (Week 20) assessment.

- Hemoglobin A1c (HbA1c) [%]

The Baseline HbA1c value will be identified as the last assessment value taken prior to the start of study medication. For most patients, this will be taken as the Screening assessment, however, if any patients have an unscheduled assessment after their Screening assessment and before starting study medication, this will be used. The change and percentage change from Baseline to the end of Period 1 (Week 8), end of Period 2 (Week 16) and Follow-up (Week 20) assessment will also be derived.

3.2.3 Pregnancy Testing

A serum pregnancy test was to be performed at Screening and Week 20, and a urine pregnancy test was to be performed at Baseline (Day 1).

3.2.4 Vital Signs

Vital signs were to be recorded at Screening and repeated at Baseline (Day 1), and at the study visit at Week 2, 4, 6, and 8 during Period 1 and at Week 10, 12, 14, and 16 during Period 2 and at the Follow-up (Week 20) assessment. Vital signs assessments would include: height (at Screening only), weight (at Screening, Week 8, 16, and 20 only), systolic and diastolic blood pressure, heart rate and temperature (all assessments).

The screening weight value will be taken as Baseline. The Baseline value for each of the remaining recurring vital signs parameters will be identified as the last assessment value taken prior to the start of study medication. For most parameters and most patients, this will be taken as the Baseline (Day 1) assessment, however, if any patients have an unscheduled assessment after their Day 1 assessment and before starting study medication, this will be used; or if a patient has a missing Day 1 value, then their Screening value will be used. The change and percentage change from Baseline to each post-Baseline assessment will be derived for each vital signs parameter.

Values from each assessment or changes from Baseline that are outside the thresholds presented below will be identified in an analysis dataset by electronic programming for reporting purposes.

	Threshold
Systolic BP (mmHg)	≥ 160
Diastolic BP (mmHg)	≥ 100
Heart Rate (bpm)	≤ 50
Heart Rate (bpm)	≥ 120
Change in Systolic BP (mmHg)	≥ 30
Change in Diastolic BP (mmHg)	≥ 30
Change in Heart Rate (bpm)	≥ 30

3.2.5 12-Lead ECG

A 12-lead ECG was to be performed at Screening, and repeated at Baseline (Day 1), and at the scheduled visits at Week 2, 4, 6, and 8 during Period 1 and at Week 10, 12, 14, and 16 during Period 2, and the Follow-up (Week 20) assessment.

At each ECG assessment, three traces were to be performed, each containing three complexes (of a single beat). From each complex, the following ECG parameters were to be reported by the ECG Corelab:

- RR [ms]
- PR [ms]
- QRS [ms]
- QT [ms]
- T-Peak (TP) [ms]
- T-wave amplitude (Tamp) [mV]
- J-Tpeak
- Tpeak-Tend

From the exported parameters listed above, the following additional parameters will be derived by statistical programming for each available complex:

$$QTcF = QT / \sqrt[3]{RR}$$

$$JTcF = QTcF - QRS$$

For each ECG parameter (RR, PR, QRS, QT, TP, T-wave, QTcF, JTcF) within each trace, a mean of the three complexes was to be derived. A mean of the three traces was then to be derived from the mean of the three complexes. This mean (of traces) of the mean (of complexes) will be presented in the ECG listings and used in the ECG descriptive statistics and analyses. Individual complexes will be available in the SDTM and ADaM datasets only and will not be presented in study listings.

ECG Corelab will also provide a Global RR value for the whole ECG trace. From this Global RR, statistical programming will derive ECG heart rate:

$$HR = 60 / [Global\ RR / 1000]$$

In addition to the above measurements, ECG Corelab was to provide an overall interpretation of the ECG. ECG traces were also to be made available to the study site Investigator, who would provide their overall interpretation and an indication of the clinical significance of any findings.

Changes in each of the ECG parameters from Baseline to each post-Baseline will be derived. The last ECG assessment prior to starting study medication will be regarded as Baseline (this will usually be the Day 1 assessment).

Assessment values or changes from Baseline that are outside the thresholds presented below will be identified in an analysis dataset by electronic programming for reporting purposes.

	Thresholds
QT (msec)	>450 >480 >500
Changes in QT (msec)	>30 >60
QTcF (msec)	>450 >480 >500
Changes in QTcF (msec)	>30 >60

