MedDRA	Medical Dictionary for Regulatory Activities
MITT	Modified Intention to Treat
msec	milliseconds
PEX	Perhexiline
PM	Poor metabolizer
PT	Prothrombin Time
PTT	Partial Thromboplastin Time
QTc	Corrected QT interval
QTcF	QT corrected according to Fridericia's formula
RBC	Red Blood Cells

SAE	Serious adverse event
SAP	Statistical Analysis Plan
TE	Treatment-Emergent
TEAE	Treatment-Emergent Adverse Event
TRANS	trans -Hydroxy-Perhexiline
ULN	Upper limit of normal
UM	Ultra-rapid metabolizer
VO ₂ MAX	Maximal oxygen consumption

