8.6 ECG Parameters

All ECG data from patients in the Safety Population will be presented in a data listing. The listing will identify the Baseline value, and present the visit value and change from Baseline to each visit value, for each parameter. Each ECG parameter will be summarized using descriptive statistics for each assessment visit using the Safety Population.

The number of patients experiencing visit values or changes from Baseline within the ranges specified in section 3.2.5 will be summarized by counts and percentages for patients in the Safety Population.

Shift tables will be used to indicate the number of patients with QT or QTcF values or changes from Baseline values that changed status relative to the thresholds identified above (section 3.2.5) between Baseline and any ECG during each period.

The change from Baseline of the QTcF interval at the end of study-drug dosing Period 1 compared to the change from Baseline at the end of study-drug dosing Period 2 will be analyzed using an ANCOVA for the Safety Population.

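### As printed, the SAP's QTcF formula omits the conversion of RR from milliseconds to seconds, so QTcF is ten times too small and JTcF is negative

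*SAP*

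**What the plan says.** SAP section 3.2.5 (12-Lead ECG) lists what the core laboratory reports for each complex, with RR, PR, QRS and QT all in ms. QTcF and JTcF are not on that list. The SAP creates them itself: "From the exported parameters listed above, the following additional parameters will be derived by statistical programming for each available complex". The two rules are QTcF = QT divided by the cube root of RR, and JTcF = QTcF minus QRS. The abbreviations list defines QTcF as "QT corrected according to Fridericia's formula" and gives no unit for RR.

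Later in section 3.2.5 the core laboratory's Global RR is used for heart rate: "From this Global RR, statistical programming will derive ECG heart rate". That formula is 60 divided by (Global RR / 1000), so the conversion to seconds is written out there.

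The derived QTcF is then flagged at ">450 >480 >500" msec, and its change from Baseline at more than 30 and more than 60 msec. SAP section 8.6 uses these values in descriptive statistics, threshold counts, shift tables and an ANCOVA that sets Period 1 against Period 2, described in these words: "The change from Baseline of the QTcF interval at the end of study-drug dosing Period 1 compared to the change from Baseline". Protocol section 8.1.2 lists that comparison as a secondary endpoint.

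**The concern.** The formula takes RR in the unit in which it is exported, and that unit does not fit the correction the SAP names. The result is on a scale that cannot be compared with the msec thresholds in the same section. JTcF fares worse, because a full-scale QRS is subtracted from a QTcF at one tenth of its scale.

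The affected outputs matter for this drug. Protocol section 2.5 reports that perhexiline prolonged QTcF in the thorough QT study, by 15.3 and 22.8 msec at the two mean peak concentrations given. The protocol adds cardiac screening and monitoring for that reason. The programmed QTcF is the only QTcF source that the SAP specifies for its listings, threshold tables and Period 1 versus Period 2 analysis. If the printed rule were followed, effects of the size seen in the thorough QT study would appear as 1.53 and 2.28 msec, and the threshold tables would be empty.

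**Working it through.** **Inputs from the documents.** RR, QT and QRS are in ms, and the two derivation formulas and the flag levels are those of SAP 3.2.5. The documents give no patient ECG values, so the RR, QT and QRS figures below are assumptions chosen to span a plausible range.

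**Scale factor.** Let R be RR in ms, so that RR in seconds is R/1000.

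- As printed: QTcF = QT / R^(1/3)
- With RR in seconds: QTcF = QT / (R/1000)^(1/3) = QT / (R^(1/3) / 10) = 10 × QT / R^(1/3)

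The ratio is exactly 10 whatever the heart rate. Averaging over complexes and traces, as the SAP does, leaves it at 10.

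**Examples (QRS 100 ms).**

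| RR (ms) | QT (ms) | QTcF as printed | QTcF with RR/1000 | JTcF as printed | JTcF with RR/1000 |
|---|---|---|---|---|---|
| 1000 | 400 | 40.0 | 400.0 | -60.0 | 300.0 |
| 900 | 420 | 43.5 | 435.0 | -56.5 | 335.0 |
| 850 | 480 | 50.7 | 506.7 | -49.3 | 406.7 |
| 600 | 480 | 56.9 | 569.1 | -43.1 | 469.1 |

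Over a grid of RR 500 to 1500 ms, QT 360 to 540 ms and QRS 80, 100 and 120 ms, printed JTcF is negative in every cell, from -12.0 to -88.6. It can be positive only if the true QTcF exceeds ten times QRS; with QRS 80 ms that means a true QTcF above 800 ms.

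**Value flags.** The QT needed to exceed a flag t under the printed rule is t × R^(1/3).

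- RR 1000 ms: 4500, 4800 and 5000 ms for the 450, 480 and 500 flags.
- RR 500 ms: 3572, 3810 and 3969 ms.

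The assumed patient with a true QTcF of 506.7 ms is therefore not flagged at any level.

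**Change flags.** A printed change above 30 or 60 needs a true change above 10 × 30 = 300 ms or 10 × 60 = 600 ms.

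**Direction of JTcF changes.** Suppose the true QTcF rises by 20 ms and QRS by 5 ms. The true JTcF change is 20 - 5 = +15 ms. The printed rule gives 20/10 - 5 = -3 ms. The sign reverses, so a simple rescaling of JTcF afterwards would not repair it.

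**Period 1 versus Period 2 ANCOVA.** Dividing every QTcF by 10 leaves the p-value unchanged and makes the estimate and its confidence interval ten times too small.

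**The case against.** The strongest reply is that all of this assumes the line is coded exactly as printed. The SAP names Fridericia's method and sets limits in the hundreds of msec, so the only coherent reading is RR in seconds, and an experienced programmer may convert without being told. QTcF values near 42 and negative JTcF in practically every patient would be hard to miss. SAP section 5.4 also places the programming and derived-database specifications in separate documents, which are not available here and may contain the conversion.

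There are limits on reach as well. The uncorrected QT flags are unaffected. The SAP flags serve reporting: under the protocol, baseline ECG eligibility is confirmed centrally (section 6.4), and dose adjustment for QTcF or JTcF is directed by the ECG core laboratory (section 4.4.4). Nothing says those decisions use the SAP-derived variable. The QTcF ANCOVA p-value would survive, and crossing a change flag is implausible rather than algebraically impossible.

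These points stand as limits on the likely damage, and none of them makes the printed rule correct. The heart-rate formula shows that the authors wrote the conversion where they intended it, so its absence cannot be read as a convention. An unseen specification does not amend the SAP, and a plan should not rely on a programmer overriding it for the drug's known safety signal.

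**Conclusion.** The formula is wrong as written. With RR in ms, derived QTcF is exactly one tenth of the intended value at every heart rate, and JTcF is negative for any plausible ECG. The 450, 480 and 500 msec flags and the 30 and 60 msec change flags cannot realistically be reached. The factor of 10 is algebra and rests on no assumption beyond the units the SAP states; the individual patient figures use assumed RR, QT and QRS values.

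The error covers the SAP-derived QTcF and JTcF: listings, summaries, QTcF threshold counts and shift tables, and the estimate and interval for the QTcF secondary endpoint. On the documents, it does not reach the uncorrected QT tables, or eligibility and dose decisions. It is a fault in the specification and does not show that any reported result was wrong. It must be corrected because it is certain as printed, it affects a secondary endpoint and the main ECG safety tables, and it costs almost nothing to repair.

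**What to change.** In SAP 3.2.5, replace the derivation with QTcF = QT[ms] / (RR[ms]/1000)^(1/3), followed by JTcF = QTcF - QRS, all in ms. Make the same correction in the programming and derived-database specifications if they repeat the printed line.

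Then compare programmed QTcF and JTcF with the values the core laboratory used for baseline confirmation and dose instructions. Those values are not on the export list in SAP 3.2.5, so they would have to be requested. If they cannot be obtained, independent double programming with a plausibility check on the range would serve.

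The cost is a one-line revision, which the SAP's Introduction allows before database lock with the reason given in the study report, plus the comparison. Design, sample size and patient procedures are unaffected.
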